8.3.1.4. Immunoglobulin Results Relative to the Lower Limit of Normal

Immunoglobulins (IgG, IgA, IgM) will be classified relative to the reference range for the following categories: < LLN and \ge LLN.

8.3.2. Summary Measure

8.3.2.1. Clinical Laboratory Results

Laboratory parameters which are continuous numeric values will be analyzed using summary statistics, and those with categorical results will be summarized using frequencies and percentages. Results will be presented by visit during the 52-week treatment phase, and at any time post-baseline where specified.

8.3.2.2. Clinical Laboratory Toxicity Grades

The frequencies and percentages of subjects meeting each of the toxicity grade endpoints will be summarized by visit during the 52-week treatment phase, and at any time post-baseline where specified.

8.3.2.3. Clinical Laboratory Reference Range Shifts

The frequencies and percentages of subjects meeting each shift criteria will be summarized by visit during the 52-week treatment phase.

8.3.2.4. Immunoglobulin Results Relative to the Lower Limit of Normal

The frequencies and percentages of subjects who are <LLN and \ge LLN will be summarized by visit during the 52-week treatment phase. The analyses will be repeated for the subgroup of patients who are \ge LLN and who are <LLN at baseline, respectively.

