5.3. Baseline Definitions

5.3.1. Baseline Definitions¹

The baseline (BL) definition is dependent upon the endpoint being analyzed.

• For the SELENA SLEDAI (including rebound), immunoglobulins, autoantibodies, complement, BLyS and B-cell endpoints, baseline is defined as the Day 0 assessment in the subject's respective parent study, prior to exposure with study treatment (whether placebo or belimumab). Baseline data for these

parameters will be extracted from the ADaM data sets from the double blind study (LBSL02, BEL110751, BEL113750 or BEL112341) from which the patients are enrolled.

- For the SLE flares, SLE severe flares, SLICC, prednisone (7 day average prior to Day 0), PGA, and immunogenicity², endpoints, baseline is the Day 0 assessment in BEL116027.
- For other endpoints, baseline is the Day 0 assessment in BEL116027².

¹Feeder study BEL114333 database had not yet completed at the time of BEL116027 Last Patient Last Visit. Consequently, baseline data for BEL114333 patients has not been fully cleaned when extracted from that study's database for reporting.

²Assessments covered for both Day 0 in BEL116027 and the Exit/Follow-up visit of the feeder continuation studies were only to be performed once and were to be recorded in the appropriate case report forms for each study. For Day 0 values not recorded in BEL116027 CRF but exist in the feeder study, the data will be extracted from the appropriate feeder study for inclusion in analysis

In the displays, the baseline value/visit will be denoted as Baseline.

See Section 13.4.1 for a diagram depicting the baseline definitions and phases.

Definition	Reporting Details
Change from Baseline	= Post-Dose Visit Value – Baseline
% Change from Baseline	= 100 x [(Post-Dose Visit Value – Baseline) / Baseline]
Maximum Change from Baseline	= Calculate the change from baseline at each given timepoint
	and determine the maximum change

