5.3.2. Derivations and Handling of Missing Baseline Data

NOTES:

 Unless otherwise specified, the baseline definitions specified in Section 5.3.1 Baseline Definitions will be used for derivations for endpoints / parameters and indicated on summaries and listings.

 Unless otherwise stated, if baseline data is missing no derivation will be performed and baseline will be set to missing.

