8.3. Clinical Laboratory Analyses

Laboratory evaluations including the analyses of chemistry laboratory tests, hematology laboratory tests, urinalysis, and liver function tests will be based on GSK Core Data Standards. The details of the planned displays are in Appendix 11: List of Data Displays.

An issue was identified at Q2 Solutions (central lab) in Valencia, California, USA, regarding equipment malfunction which affected some serum creatinine results reported from one of the analyzers used at the lab. Unusually high serum creatinine results were noted for two different GSK clinical trials, and further investigation revealed one of the analyzers had been producing intermittent high serum creatinine results between 01 October 2016 to 13 January 2017, potentially due to an intermittent wash line blockage of the analyzer. BEL116027 investigators were notified of this issue by a Dear Investigator Letter (DIL) 22 February 2017. The subsequent evaluation concluded that there was no impact on data integrity and patient safety for clinical trial BEL116027. Therefore, there will be no modification to the analysis of serum creatinine. BEL116027 investigators were notified by a follow up DIL dated 25 July 2017, and the root cause was identified as a sporadic failure of the wash system due to debris causing intermittent obstruction.

Baseline is defined as described in Section 5.2.

A list of laboratory parameters collected and definition of the toxicity grades are provided in Appendix 8: Values of Potential Clinical Importance.

Listings will be generated for all laboratory results, and additionally for Grade 3 or Grade 4 laboratory toxicity results.

Line graphs will be produced for each analyte displaying the mean value by visit and treatment group.

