13.4.1.2. Treatment Control Group

Endpoint	Day 0 Visit Parent Study	Day 0 Visit BEL116027 Study [1]	Week 24 Visit	Week 52/ Exit Visit	Week 16 Follow -up Visit				
		Baseline							
Flare, PGA, Prednisone, SLICC	N/A	52-Week Trea	atment Phase	Maintenance Phase	N/A				
Baseline									
SS, Auto-antibodies Immunoglobulins, B-cells [2], BLyS	Pre-Study Phase	52-Week Trea	atment Phase	Maintenance Phase	N/A				
		Baseline		•					
Rebound [3]		52-Week Trea	atment Phase						
	Pre-Study Phase	First 24 Weeks	N/A	N/A	N/A				
		Baseline		•					
Adverse Events, Lab Parameters, Vital Signs, Con Meds, Immunogenicity [2]	N/A	52-Week Trea	atment Phase	Maintenance Phase	N/A				

N/A = Not Applicable.

[1] If the first infusion date differs from the Day 0 visit date, then the first infusion date will be used as the phase cut-point.

[2] Immunogenicity and B-cells may also be collected at the 6-month follow-up visit. The 6-month follow-up visit is not represented in the diagram since it does not define a treatment phase of the study.

[3] Rebound is only assessed up to the Week 24 visit.

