3.21.	ITT	Adverse Events of Special Interest by Category (52-Week Treatment Phase)	Benlysta Standard	н		
3.22.	ITT	Adverse Events of Special Interest by Category and Infusion for Treatment Holiday Group Re-Start Phase	Benlysta Standard			
Labora	tory Parameter	'S				
3.23.	ITT	Laboratory Results by Visit: Hematology (52-Week Treatment Phase				
3.24.	ITT	Laboratory Results by Visit: Liver Function (52-Week Treatment Phase)				
3.25.	ITT	Laboratory Results by Visit: Electrolytes (52-Week Treatment Phase)				
3.26.	ITT	Laboratory Results by Visit: Other Chemistries (52-Week Treatment Phase)				
3.27.	ITT	Laboratory Results by Visit: Urinalysis (52-Week Treatment Phase)				
3.28.	ITT	Laboratory Results by Visit: Immunoglobulins (52-Week Treatment Phase)				
3.29.	ITT	Worst Laboratory Toxicity Grade: Hematology (52-Week Treatment Phase)	ICH E3			

Safety:	Tables			
No.	Population	Title	Programming Notes	Priority Headline Results Denoted by H
3.30.	ITT	Worst Laboratory Toxicity Grade: Liver Function (52-Week Treatment Phase)	ICH E3	
3.31.	ITT	Worst Laboratory Toxicity Grade: Electrolytes (52-Week Treatment Phase)	ICH E3	
3.32.	ITT	Worst Laboratory Toxicity Grade: Other Chemistries (52-Week Treatment Phase)	ICH E3	
3.33.	ITT	Worst Laboratory Toxicity Grade: Urinalysis (52-Week Treatment Phase)	ICH E3	
3.34.	ITT	Worst Laboratory Toxicity Grade: Immunoglobulins (52-Week Treatment Phase)	ICH E3	
3.35.	ITT	Laboratory Toxicity Grade Worsening of at Least 2 Grades from Baseline: Hematology (52-Week Treatment Phase)	Benlysta Standard	
3.36.	ITT	Laboratory Toxicity Grade Worsening of at Least 2 Grades from Baseline: Liver Function (52-Week Treatment Phase)	Benlysta Standard	
3.37.	ITT	Laboratory Toxicity Grade Worsening of at Least 2 Grades from Baseline: Electrolytes (52-Week Treatment Phase)	Benlysta Standard	
3.38.	ITT	Laboratory Toxicity Grade Worsening of at Least 2 Grades from Baseline: Other Chemistries (52-Week Treatment Phase)	Benlysta Standard	
3.39.	ITT	Laboratory Toxicity Grade Worsening of at Least 2 Grades from Baseline: Urinalysis (52-Week Treatment Phase)	Benlysta Standard	
3.40.	ITT	Laboratory Toxicity Grade Worsening of at Least 2 Grades from Baseline: Immunoglobulins (52-Week Treatment Phase)	Benlysta Standard	
3.41.	ITT	Laboratory Reference Range Shifts from Baseline by Visit: Hematology (52-Week Treatment Phase)	Benlysta Standard	

Safety: Tables				
No.	Population	Title	Programming Notes	Priority Headline Results Denoted by H

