3.42.	ITT	Laboratory Reference Range Shifts from Baseline by Visit: Liver Function (52-Week Treatment Phase)	Benlysta Standard	
3.43.	ITT	Laboratory Reference Range Shifts from Baseline by Visit: Electrolytes (52-Week Treatment Phase)	Benlysta Standard	
3.44.	ITT	Laboratory Reference Range Shifts from Baseline by Visit: Other Chemistries (52-Week Treatment Phase)	Benlysta Standard	
3.45.	ITT	Laboratory Reference Range Shifts from Baseline by Visit: Urinalysis (52-Week Treatment Phase)	Benlysta Standard	
3.46.	ITT	Laboratory Reference Range Shifts from Baseline by Visit: Immunoglobulins (52-Week Treatment Phase)	Benlysta Standard	
Immun	oglobulins			
3.47.	ITT	Immunoglobulin Levels below the Lower Limit of Normal (LLN) by Visit (52-Week Treatment Phase)	Benlysta Standard	
3.48.	ІТТ	Immunoglobulins below the Lower Limit of Normal (LLN) at each Visit among Subjects with Immunoglobulins >= LLN at Baseline (52-Week Treatment Phase)	Benlysta Standard	
3.49.	ITT	Immunoglobulins above the Lower Limit of Normal (LLN) at each Visit (52-Week Treatment Phase)	Benlysta Standard	
3.50.	ITT	Immunoglobulins above the Lower Limit of Normal (LLN) at each Visit among Subjects with Immunoglobulins <= LLN at Baseline (52-Week Treatment Phase)	Benlysta Standard	
Immun	ogenicity			
3.51.	ITT	Immunogenic Response by Visit (52-Week Treatment Phase)	Benlysta Standard	

Safety:	Safety: Tables					
No. Population Title Programming Notes Priority Denoted by H				Headline Results		
Vital Sig	Vital Signs					
3.52.	ITT	Vital Signs Change from Baseline by Visit (Observed) (52-Week Treatment Phase)	ICH E3			

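### The SAP gives conflicting baselines for the immunoglobulin safety tables, and its more specific rule would book changes from earlier belimumab treatment to this study's 52-week phase

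*SAP*

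**What the plan says.** SAP 5.3.1 sets baseline by endpoint. Its first rule reads: "For the SELENA SLEDAI (including rebound), immunoglobulins, autoantibodies, complement, BLyS and B-cell endpoints, baseline is defined as the Day 0 assessment". The study meant is each subject's parent study, before any study treatment. Endpoints not named take BEL116027 Day 0. SAP 5.3.2 makes this the default where nothing else is stated: "the baseline definitions specified in Section 5.3.1 Baseline Definitions will be used for derivations for endpoints / parameters and indicated on summaries and listings".

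The laboratory safety section, SAP 8.3, does not specify otherwise. It says "Baseline is defined as described in Section 5.2", but Section 5.2 lists parent and continuation studies and contains no baseline definition. For the LLN analyses, SAP 8.3.2.4 adds "The analyses will be repeated for the subgroup of patients who are" in either LLN category at baseline, without naming which baseline.

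The phase diagrams in SAP 13.4.1 point both ways. The row "SS, Auto-antibodies Immunoglobulins, B-cells [2], BLyS" (control-group version) carries a pre-study phase that starts at parent-study Day 0. A separate row for adverse events, laboratory parameters and vital signs has its baseline at BEL116027 Day 0. In SAP 13.3.3, the analysis visit labelled baseline is Study Day 1 of BEL116027.

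Four listed safety displays depend on this choice, all labelled for the 52-week treatment phase:
- Table 3.40, "Laboratory Toxicity Grade Worsening of at Least 2 Grades from Baseline: Immunoglobulins (52-Week Treatment Phase").
- Table 3.46, reference range shifts from baseline for immunoglobulins.
- Table 3.48, "Immunoglobulins below the Lower Limit of Normal (LLN) at each Visit among Subjects with Immunoglobulins >= LLN at Baseline".
- Table 3.50, the counterpart for subjects low at baseline.

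**The concern.** A safety table labelled for the 52-week phase will be read as describing what happened in that phase. At least 6 months of belimumab separates the two candidate baselines (Protocol 4.2). Protocol 1.1 says the drug reduces differentiation of B cells into immunoglobulin-producing plasma cells, so a fall before entry is plausible.

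The study exists to describe withdrawal. The long-term discontinuation group receives no belimumab here, and the holiday group is planned to receive none before Week 24 (Protocol 5.1). With a pre-belimumab reference, either group could show an apparent immunoglobulin toxicity while values are stable or recovering off drug. Prior exposure also differs between groups: only the discontinuation group draws on HGS1006-C1066 and LBSL99, which carry 5-year and 10-year treatment commitments (Protocol 3.2). A between-group comparison would then partly reflect treatment history before Day 0.

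**Working it through.** The plan states no figure to reproduce. The check traces the rule to each table and then classifies one IgG course under each baseline.

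**Which isotype reaches which table**
- SAP 13.8.2 grades only IgG: Grade 1 is 550-700 mg/dL, Grade 2 400-549, Grade 3 250-399 and Grade 4 below 250. Table 3.40 can therefore concern only IgG.
- SAP 8.3.1.3 limits shift summaries to tests without toxicity grades. Table 3.46 therefore concerns IgA and IgM.
- Tables 3.48 and 3.50 use the LLN for all three isotypes: IgG 6.94, IgA 0.81 and IgM 0.48 g/L (SAP 13.6.6.1).

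**Illustrative IgG course** (mg/dL = 100 × g/L; change = grade at visit − grade at baseline)

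| Time | g/L | mg/dL | Grade | Below 6.94 g/L? | Change from parent Day 0 | Change from BEL116027 Day 0 |
|---|---|---|---|---|---|---|
| Parent Day 0 | 8.0 | 800 | 0 | no | – | – |
| BEL116027 Day 0 | 5.4 | 540 | 2 | yes | – | – |
| Week 8 | 5.45 | 545 | 2 | yes | 2 − 0 = +2 | 2 − 2 = 0 |
| Week 24 | 6.0 | 600 | 1 | yes | 1 − 0 = +1 | 1 − 2 = −1 |

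From the parent baseline, this subject meets the 2-grade criterion at Week 8 (Table 3.40). At both visits the subject is also below the LLN within the subgroup normal at baseline (Table 3.48). From BEL116027 Day 0 there is no worsening, and the subject belongs to the low-at-baseline subgroup.

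**Other tables**
- Table 3.46: an IgM value at or above 0.48 g/L at parent Day 0, but below it at BEL116027 Day 0 and afterwards, is a shift to low from the parent baseline and no shift from Day 0.
- Table 3.50: for IgG of 12, 5.2 and 7.5 g/L at parent Day 0, BEL116027 Day 0 and a later visit, the recovery occurs in this study. The parent baseline puts the subject in the normal subgroup, so Table 3.50 misses that recovery.
- Specificity: for IgG of 12, 12 and 5.2 g/L, both baselines count the 2-grade fall. Changing to Day 0 does not lose a true in-study event of this kind.

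**Possible size**

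Enrolled numbers are 12 holiday, 29 control and 39 discontinuation (SAP 2.3). One subject is 1/12 = 8.3%, 1/29 = 3.4% or 1/39 = 2.6% of the group. Let q be the share at or above the LLN at parent Day 0 but below it at BEL116027 Day 0, with no change afterwards. The documents do not give q; 5%, 10% and 20% are assumptions. The expected number in Table 3.48 under the parent baseline is n × q.

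| Group | q = 5% | q = 10% | q = 20% |
|---|---|---|---|
| Holiday, n = 12 | 0.6 | 1.2 | 2.4 |
| Control, n = 29 | 1.5 | 2.9 | 5.8 |
| Discontinuation, n = 39 | 2.0 | 3.9 | 7.8 |

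The chance of at least one such holiday subject is 1 − (1 − q)^12, which gives 0.46, 0.72 and 0.93. With BEL116027 Day 0 as baseline, every count in the table is 0.

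**The case against.** The strongest reply is that the safety tables may never have been meant to use the parent baseline. SAP 2.2 lists laboratory parameters under safety and immunoglobulins under markers of autoimmune response. The 5.3.1 rule could therefore cover only the marker endpoints, leaving the safety tables with the laboratory row of 13.4.1 and the Study Day 1 baseline visit of 13.3.3. This stands to the extent that the text conflicts. A reader might infer that the SAP settles on the parent baseline and that wrong counts are certain; the documents do not support that. They do name immunoglobulins explicitly under the parent baseline, apply that by default, and give no exception in 8.3, so it is the more specific instruction.

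A reader might also infer that all four tables count worsening, or that an IgG fall below the LLN enters the shift table. Neither follows. Tables 3.48 and 3.50 report status within a baseline subgroup, and 8.3.1.3 keeps IgG out of Table 3.46.

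Other displays allow a partial cross-check. Tables 3.28, 3.34, 3.47 and 3.49 do not depend on baseline, Listing 33 gives individual results, and SAP 11.1.2.2 shows biomarker change at the Day 0 visit. A careful reader could separate a low value at entry from a later fall, but the four affected tables would still mislead when read alone.

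Finally, the pre-belimumab reference has a protocol basis (Protocol 6.1.2) and is informative about cumulative change. That supports keeping it for the biomarker endpoint, where the protocol places it. It does not make it the right reference for safety events of this study's 52 weeks.

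**Conclusion.** The concern holds as a conflict in the baseline definition whose more specific reading misattributes change that predates entry. Under that reading, Table 3.40 (IgG) and Table 3.46 (IgA and IgM) would count pre-entry changes as worsening in the 52-week phase. Tables 3.48 and 3.50 would define subgroups by status before belimumab rather than at entry.

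The number of subjects affected is unknown. The IgG course and the values of q are illustrations, and a reader should not infer from them that many subjects are misclassified. The study is descriptive (SAP 2.4), so no test or decision rule is affected. With 12 holiday subjects, however, a single misplaced subject moves a percentage by 8.3 points. The SAP should resolve this before the tables are produced.

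**What to change.** In SAP 5.3.1 and 8.3, state that Tables 3.40, 3.46, 3.48 and 3.50 use the BEL116027 Day 0 immunoglobulin value. If the pre-belimumab comparison is also wanted there, show it as a second, labelled baseline. Keep the parent-study baseline for biomarker Tables 5.11-5.15. Correct the reference to Section 5.2 in SAP 8.3, and align the 13.4.1 diagrams by separating immunoglobulins as biomarkers from immunoglobulins as laboratory safety parameters.

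The cost is SAP wording and one additional baseline flag in the analysis dataset. IgG, IgA and IgM are already scheduled at Day 0 (Protocol Table 2), so no new samples are needed. The small downside is that, if only the Day 0 baseline is shown, cumulative change since before belimumab must be read from the biomarker tables.

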8.3.3. Population of Interest

For all clinical laboratory endpoints, the analyses will be based on the ITT population.

8.3.4. Strategy for Intercurrent (Post-Randomization) Events

For all clinical laboratory endpoints, observed data will be used with no imputation.

8.3.5. Statistical Analyses / Methods

Details of the planned displays are provided in Appendix 11: List of Data Displays and will be based on GSK data standards and statistical principles.

Unless otherwise specified, endpoints / variables defined in Section 8.3.1 will be summarised using descriptive statistics, graphically presented (where appropriate) and listed.

8.4. Other Safety Analyses

The analyses of non-laboratory safety test results including immunogenicity and vital signs will be based on GSK Core Data Standards, unless otherwise specified. The details of the planned displays are presented in Appendix 11: List of Data Displays.

8.4.1. Endpoint / Variables

8.4.1.1. Immunogenicity

Serum samples for anti-belimumab antibody measurements will be obtained from subjects per the protocol

For the immunogenicity assessment, two types of antibody assays will be performed, i.e. a binding assay and neutralizing assay. For the binding assay, there will be 3-testing steps. A screening assessment is performed which produces a result of positive or negative. For samples with a positive screening result, a confirmation assay is then carried out, which also produces a result of positive or negative. For samples with a positive screening result, a confirmation assay is then positive confirmation result, a titer value will also be obtained to quantify the degree of binding in a titration assay step. Patients will be viewed as positive for the binding assay if the confirmation assay was positive. Subjects, who tested positive for the binding assay, will be tested for the neutralizing assay, which again produces a result of positive or negative.

8.4.1.2. Vital signs

Vital signs will be collected per the protocol. Parameters along with units for reporting are listed below.

Vital Sign Parameter (Units)
Systolic Blood Pressure (sitting) (mmHg)
Diastolic Blood Pressure (sitting) (mmHg)
Heart Rate (beats/min)
Temperature (C)
Weight (kg)
BMI (kg / m ²)

8.4.2. Summary Measure

8.4.2.1. Immunogenicity

Immunogenic response will be summarized by visit and anytime postbaseline for the 52-week treatment phase.

Categories of response are Negative, Transient Positive (defined as a single positive response that does not occur at the final assessment, or Persistent Positive (defined as a positive response that occurs on at least 2 consecutive assessments or a single result at the final assessment).

